**Truncal ultrasound guided regional anesthesia for implantation and revision of
AICDs and pacemakers in pediatric patients**

NCT04184349

Version Date: 12/19/2019

Title: Truncal ultrasound guided regional anesthesia for implantation and revision of AICDs and pacemakers in pediatric patients.

PI: [name] (Anesthesiologist)

Co PIs: [name] (Electrophysiologist), [name] (Electrophysiologist), [name] (Anesthesiologist), [name] (Anesthesiologist), [name] (Anesthesiologist), [name] (Anesthesiologist)

Population: Children undergoing pacemaker and/or Automatic Implantable Cardioverter Defibrillator implantation at Children's Memorial Hermann Hospital

Study Duration: Data will be collected from procedure for 48 hours

Purpose

The purpose of this study is to determine the efficacy and safety of truncal blocks for pacemaker and Automatic Implantable Cardioverter Defibrillator implantation in children

Hypothesis Truncal block is effective, safe and feasible for implantation of AICDs and pacemakers in children.

Research Design and Procedures to be Used

Written consent for the study will be obtained from a parent. We will also obtain consent from the patient if they are older than 10 years together with their parents.

The patients will be simply randomized by a pre-determined computer generated random numbers and allocated to one of two groups. The group allocation (LA group or B group) will be concealed in sealed opaque envelopes that will be opened after enrollment of the patients. In one group (the LA group), only the local anesthetic infiltration will be performed. In the block group (the B group), PECS and TTP blocks will be performed. The ultrasound-guided nerve blocks will be performed by the anesthesiologist after induction of anesthesia and endotracheal intubation. The left upper extremity angiogram will be performed prior to block to ensure the correct side for the implant. The local anesthetic group will have wound infiltration as routine care by the electrophysiologist at the time of wound closure. Both of these blocks have been used successfully in our institution and the purpose of the study is to prospectively evaluate whether there is a decrease in amount of narcotic medications need and track complications. There is no deviation from the standard of care as currently practiced.

At our institution, the incision is typically made below the clavicle on the left anterior chest wall and a subcutaneous (pre-pectoralis major) pocket or sub-muscular pocket is created between pectoralis major and minor muscles with sharp and blunt dissection and electrocautery by the electrophysiologist. Based on the literature this area is best covered by a PECS block combined with the transversus thoracic muscle plane block to help cover medial anterior nerve branches. (5) The adult literature describes mainly a combination of serratus plane block combined with transversus thoracic plane block as the generator is placed in the mid axillary line. (4). The dose of 0.2% ropivacaine is 1ml/kg and so for the block group the dose is divided into halves for the PECS block and TTP block (2 injections). For ultrasound-guided peripheral nerve block, we will

use a 22-gauge 4 cm Pajunk needle and a linear probe of the SonoSite. The skin will be cleaned with chlorhexidine prep solution and aseptic technique followed.

Pecs Block

The goal of the Pecs block is to infiltrate the fascial compartment with local anesthetic ropivacaine between the pectoral nerves (the pectoral fascia and clavipectoral fascia). The local anesthetic should cover the pectoral compartment with the pectoral nerves. The block is performed with the patient supine, either with the arm abducted 90 degrees or by his or her side. The transducer is then moved laterally until the pectoralis minor and serratus anterior are identified. With further lateral transducer movement, the third and fourth rib can then be identified. The injection of 0.5 mL/kg of 0.2% ropivacaine is made between the pectoralis major and minor muscles.(Figure 2).

TPP block

A transversus thoracic plane block is added to provide sufficient analgesia to the area around the sternum. The ultrasound is placed on the left parasternal border at T3-4 level and moved medially until the plane between the internal intercostal and transversus thoracis muscles is identified immediately medial to the sternal border. Using an in-plane technique, 0.5mL/kg of 0.2% ropivacaine is injected between the internal intercostal and transversus thoracis muscle plane. (Figure 3).

The adjunctive medication protocol will include scheduled alternating ibuprofen and tylenol unless contraindicated by renal impairment. Both groups of patients will also have oral oxycodone available as needed for moderate breakthrough pain and IV morphine for severe pain. The total dose of local anesthetic for group B will be same as that of group LA.

Primary outcome: We will compare the two groups on their total narcotic dose in milligram morphine equivalents (MME) needed for 48 hours after procedure. This is calculated as intravenous fentanyl (mcg) x0.03+intravenous hydromorphone (mg)x20+intravenous morphine(mg)x3+[number of oral oxycodone 5 mg/acetaminophen 325 mg tabs equivalents]. The 48 hour mark is picked since the local anesthetic duration for either local infiltration or block is 6-12 hours and most patients would be discharged prior to the 48 hour mark. This also allows for sufficient time for complications to develop and tracked as secondary outcomes.

Secondary outcome: VAS pain score in PACU, incidence of pruritus, nausea/vomiting, respiratory depression, local anesthetic toxicity and pneumothorax, these complications would arise early in the post procedure period but would be tracked for 48 hours.

Statistical Analysis

Data will be analyzed within one month after completion of data collection for all enrolled patients. The de-identified data will be uploaded to PI's UTH-Share account and shared with the statistician. We will report the summary statistics of demographics and disease-related characteristics for two groups. The primary endpoint, amount of morphine equivalent administered intra-operative and during the first 24 hours after procedure, will be summarized as median and inter-quartile, and depicted as side-by-side boxplot. Comparison between two groups will be evaluated by Wilcoxon rank sum test. We will report the incidence rates of side effects including pruritis and nausea, as

well as complications including local anesthetic toxicity and pneumothorax. The Wald test will be used for comparing incidence rates between two groups.

At our institution we performed 24 implants in the last 2 years (aicd/ppm, external, 4 were lead revisions, generator changes or pocket revisions. The most common approach used is the left intra-clavicular subcutaneous (pre-pectoral). We anticipate at least 12 patients per year going forward. Based on a 5% two-sided two-sample t test, the size of 12 patients per group provides the power of 94% for detecting difference for effect size 1.5 assuming that the primary endpoint follows a normal distribution

Data and Safety Monitoring:

Both groups will be followed for signs of local anesthetic toxicity, pneumothorax or infection, these will be reviewed at quarterly intervals with the cardiologist/anesthesiologist PIs.

Risks and Potential Benefits

The risks of wound infiltration (LA group) is the potential use of higher doses of narcotic which is associated with more nausea, pruritis and potential for respiratory depression. The block groups use has the risks of insufficient analgesia with the need for rescue medications, the use of a longer block needle has the theoretical risk of injury to deeper structures such as the lung but the use of ultrasound and experience with ultrasound of the anesthesiologist makes it a minimal risk. Risks with either technique are those associated with any injection: infection, bleeding and damage to surrounding structures. Both groups have the risk of local anesthetic toxicity.

The benefit of the block group is the improved analgesia and decrease in the narcotic dose needed with a resulting decrease in narcotic associated side effects.

The secondary outcomes will be incidence of pruritus, nausea/vomiting

Importance of Knowledge That May Be Reasonably Expected To Result

Truncal ultrasound guided blocks are gaining popularity due to their efficacy in the adult population for implantation of pacemakers and AICDs and so far there is a lack of reports of these being used in the pediatric population. Based on our experience with effectiveness of truncal blocks so far we anticipate encouraging other centers to integrate this modality and offer better pain control to their patients.

Ethics

The study has obtained departmental IRB approval and is seeking institutional IRB approval. Given very positive results from the adult population, we believe delaying this study will deprive large groups of children at other institutions from receiving a pain management technique that will improve their comfort and decrease the amount of narcotic needed.

The consent and assent will be explained to family and patient and alternatives which include no randomization will be offered.

A linking log will be used to deidentify data and a data sheet have been attached for review. The data sheets will be securely destroyed as soon as deidentified data is transferred to a electronic form on a secure server. The linking log will be stored in a locked cabinets within a locked office at the medical school.

Any complications will be reviewed quarterly with the EP cardiology/anesthesiology group and will be referred for departmental quality review if there is an increase in the number of complications compared to current base line when both the pain management injections are currently performed as standard of care.

References

1. Miller, Marc ; Garg, Jalaj ; Salter, Benjamin ; Brouwer, Thomas ; Mittnacht, Alex ; Montgomery, Morgan ; Honikman, Rafael ; Arkonac, Derya ; Choudry, Subbarao ; Dukkipati, Srinivas ; Reddy, Vivek ; Weiner, Menachem. Feasibility of subcutaneous implantable cardioverter-defibrillator implantation with opioid sparing truncal plane blocks and deep sedation. *Journal of Cardiovascular Electrophysiology*, Jan 2019, Vol.30(1), p.141
2. (Bashandy, GM and Abbas, DN. Pectoral nerves I and II blocks in multimodal analgesia for breast cancer surgery: a randomized clinical trial. *Reg Anesth Pain Med*. 2015; 40: 68–74;
4. Raza, Syed M. ; Vasireddy, Appa Rao ; Candido, Kenneth D. ; Winnie, Alon P. ; Masters, Robert W. A complete regional anesthesia technique for cardiac pacemaker insertion. *Journal of Cardiothoracic and Vascular Anesthesia*, 1991, Vol.5(1), pp.54-56

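### No masking is described after the envelope is opened, so expectation could contribute to a difference in as-needed postoperative opioid

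*Combined protocol and SAP*

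**What the plan says.** Under Research Design and Procedures to be Used, the group is "concealed in sealed opaque envelopes that will be opened after enrollment of the patients". The text does not say who opens the envelope, where, or who is then told.

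The same section gives the timing of the two treatments. For the block group: "The ultrasound-guided nerve blocks will be performed by the anesthesiologist after induction of anesthesia and endotracheal intubation". The LA group has "wound infiltration as routine care by the electrophysiologist at the time of wound closure".

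The adjunctive medication paragraph, just before the Primary outcome paragraph, states: "Both groups of patients will also have oral oxycodone available as needed for moderate breakthrough pain and IV morphine for severe pain". It names no scorer and no score that separates the two levels of pain. It also states: "The total dose of local anesthetic for group B will be same as that of group LA".

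The primary endpoint is defined twice. The Primary outcome paragraph has "total narcotic dose in milligram morphine equivalents (MME) needed for 48 hours after procedure". Statistical Analysis has "amount of morphine equivalent administered intra-operative and during the first 24 hours after procedure". The secondary outcomes include a VAS pain score in PACU, pruritus and nausea or vomiting, again with no named assessor.

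Risks and Potential Benefits names better analgesia and a lower opioid dose as the benefit of the block. No section mentions masking or blinding of anyone.

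**The concern.** Sealed envelopes stop the person enrolling a child from choosing the group. They do nothing about events after they are opened. Here the postoperative part of the endpoint is a series of judgments: the child or parent reports pain, a nurse grades it, and an opioid is given or withheld. If those people know the group and share the protocol's belief that the block works, opioid use in the block group may fall for that reason alone. The PACU pain score and the subjective side effects are exposed in the same way.

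The Primary outcome paragraph expects most children to be discharged before 48 hours, so a parent may make some of these judgments at home.

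At stake is how far an observed opioid difference can be credited to the block. Masking the postoperative period looks feasible, because the block is given to an anesthetized child and the infiltration is done at the end of the procedure.

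**Working it through.** **Step 1. What each safeguard covers.**

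| Stage | Who influences the outcome | Safeguard in the documents |
|---|---|---|
| Enrollment | Person recruiting | Sealed opaque envelope |
| Intra-operative opioid | Anesthesiologist, who performs the block | None described; cannot readily be masked |
| PACU and ward opioid, VAS, side effects | Child, parents, nurses, recorder | None described; masking looks feasible |
| After discharge, up to 48 h | Child, parents | None described; masking looks feasible |

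Under the 48-hour definition, the whole endpoint is postoperative. Under the Statistical Analysis definition, it is intra-operative opioid plus 24 hours. The documents do not give the split between those two parts.

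**Step 2. Reproduce the plan's own figure.** Inputs from Statistical Analysis: n = 12 per group, two-sided 5% two-sample t test, effect size d = 1.5.

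- Degrees of freedom: 2 × 12 − 2 = 22; critical t = 2.074.
- Noncentrality: d × √(n/2) = 1.5 × √6 = 3.674.
- Power from the noncentral t: 93.9%, against the stated 94%. It reproduces.

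**Step 3. Same formula, no true effect, expectation shift b.** Set the true effect to 0 and let knowledge of the group lower opioid given in the block group by b SD. The noncentrality is then b × √6. The values of b are assumptions. The Wilcoxon column, for the planned test, is from 20,000 simulated trials with normal data and 12 per group.

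| b (SD) | b × √6 | t test significant | Wilcoxon significant |
|---|---|---|---|
| 0 | 0 | 5.0% | 4.4% |
| 0.25 | 0.612 | 9.0% | 8.2% |
| 0.5 | 1.225 | 21.6% | 19.6% |
| 0.75 | 1.837 | 42.0% | 38.9% |
| 1.0 | 2.449 | 64.9% | 60.5% |

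At b = 0.25 the 9.0% is made up of 8.5% favoring the block and 0.5% against it. From b = 0.5 upward, essentially all significant results favor the block.

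**Step 4. Scale.** A shift of 0.5 SD is 0.5/1.5 = one third of the effect the trial is sized for, yet it multiplies the error rate by 21.6/5 = 4.3. In the other direction, t-test significance needs an observed difference of about 2.074 × √(2/12) = 0.85 SD. If the observed difference were 1.5 SD, a 0.5 SD shift would account for a third of it.

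**The case against.** The strongest objection is that silence is not a statement. The documents do not declare the trial open-label, and a site could open the envelope in the procedure room, tell no one outside it, and still follow the text. A reader might infer that nobody is masked and that nurses and families know the group. The documents do not say that. They support only that no masking is described. This part of the objection stands. It does not remove the point, because a plan that is silent lets the group be known to those who generate the endpoint.

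Second, anesthesia during treatment is explicit only for the block. For the infiltration it is inferred from its timing at wound closure. The inference is reasonable but remains an inference.

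Third, masking does not cover everything. A reader might infer that it would protect the primary endpoint as a whole. It cannot protect intra-operative opioid, which Statistical Analysis counts.

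Fourth, the error rates in the table would apply to any unmasked comparison of this size. They rest on assumed shifts and normal data, although the plan uses medians and a rank test. They are not evidence about this trial.

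Fifth, this is a small single-center comparison of two techniques already in routine use there, and an openly declared unmasked design with a stated limitation would be legitimate. That is fair, but the documents make no such declaration either.

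**Conclusion.** The point holds in this form: concealment is described only up to the opening of the envelope, no masking is described after that, and postoperative opioid given on perceived pain is open to expectation that the protocol itself states in one direction.

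The size is unknown. The false-positive rates of about 9% to 65% (8% to 60.5% by Wilcoxon) are a sensitivity range for assumed shifts of 0.25 to 1.0 SD. They assume no true effect, normal data and exactly 12 per group. They show how far the error rate could move, not that it will.

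A reader might also infer that a positive result could not be attributed to the block at all. The documents do not support that. A difference near the planned 1.5 SD would be weakened by a modest shift, not made uninterpretable. The missing masking is worth correcting because the remedy is cheap and leaves the sample size and the 94% power unchanged.

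**What to change.** Add a masking paragraph that says who is unaware of the group, how, and until when:

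- Open the envelope in the procedure room after induction.
- Keep the allocation from the child, parents, PACU and ward nurses, and whoever records pain scores and side effects, until 48 h.
- Put identical dressings over the wound and block sites in both groups. The parasternal injection lies away from the incision, so a puncture mark could reveal the group.
- Keep the allocation and the times of local anesthetic administration out of the records those staff routinely see. A time before incision or at closure would give the group away. The total dose would not, since it is to be equal.
- Keep a sealed allocation card available for clinical need.
- State that the anesthesiologist and electrophysiologist are unmasked.

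Reconcile the two primary endpoint definitions, and report any intra-operative component separately as unmasked. If masking is judged impracticable, declare the trial open-label and state the limitation.

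The cost is an added dressing on LA-group children and a less detailed handover. Because the block carries its own needle-related risk, the clinical team must agree to the handover content. Both groups are already followed for the same complications, and the card covers urgent need. No extra staff or patients are required.

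### The single primary endpoint is given two different time windows (48 hours after the procedure, or intra-operative plus the first 24 hours), and nothing says which governs

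*Combined protocol and SAP*

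**What the plan says.** The plan defines its one primary endpoint twice, in adjacent parts of the same document.

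- **Primary outcome:** "We will compare the two groups on their total narcotic dose in milligram morphine equivalents (MME) needed for 48 hours after procedure". The paragraph explains the choice of 48 hours by the 6 to 12 hour duration of the local anesthetic and by the expectation that "most patients would be discharged prior to the 48 hour mark".
- **Statistical Analysis:** "The primary endpoint, amount of morphine equivalent administered intra-operative and during the first 24 hours after procedure". This is the version attached to the median and inter-quartile summary, the boxplot and the Wilcoxon rank sum test. It is not labelled secondary or sensitivity.

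Three other places bear on the window:

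- **Study Duration** (front matter): "Data will be collected from procedure for 48 hours".
- **Conversion formula** (Primary outcome): "This is calculated as intravenous fentanyl (mcg) x0.03+intravenous hydromorphone (mg)x20+intravenous morphine(mg)x3", plus a term for oral oxycodone tablets. The paragraph on adjunctive medication just before it names only two as-needed opioids: "Both groups of patients will also have oral oxycodone available as needed for moderate breakthrough pain and IV morphine for severe pain".
- **Sample size** (end of Statistical Analysis): "the size of 12 patients per group provides the power of 94% for detecting difference for effect size 1.5", with no mean, standard deviation or window.

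**The concern.** A trial with one primary endpoint needs one definition of it. Here a reader of the outcome paragraph and a reader of the analysis section would compute different totals from the same patients. Because data are collected for 48 hours, both totals are likely to be obtainable, so the choice stays open until after the results are known.

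The two versions also answer different questions. Under Research Design and Procedures, the block is given after induction and intubation, whereas for the comparator "The local anesthetic group will have wound infiltration as routine care by the electrophysiologist at the time of wound closure". Intra-operative opioid is therefore largely given while only the block group has had its study injection. That may be a genuine part of the strategy being compared, but whether it counts has to be fixed beforehand. At the other end, hours 24 to 48 lie beyond the stated 6 to 12 hour duration of the local anesthetic. The group difference need not be the same in the two totals.

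**Working it through.** **1. The definitions side by side**

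| | Primary outcome | Statistical Analysis |
|---|---|---|
| End of window | 48 h after procedure | 24 h after procedure |
| Intra-operative opioid | Not mentioned; the wording runs from after the procedure | Included |
| Called primary | Yes | Yes |
| Reason given | Yes | No |
| Tied to the planned test | Says only that groups are compared | Yes (Wilcoxon) |

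The difference in the end of the window is unambiguous. The difference over intra-operative opioid is less clear. The first definition excludes it on its face, yet its formula counts intravenous fentanyl and hydromorphone, neither of which is among the as-needed opioids named. The Study Duration line starts at the procedure and does not resolve this.

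**2. The plan's own power figure**

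Inputs from the sample-size paragraph: 12 per group, two-sided 5%, standardised effect 1.5, t test.

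- Degrees of freedom = 12 + 12 − 2 = 22.
- Noncentrality = 1.5 × √(12/2) = 3.674.
- Power from the noncentral t distribution = 0.939.

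The stated 94% reproduces. Because it rests only on a standardised effect, it fits either window and cannot identify the one intended.

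**3. Size of a single planned test**

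The exact null distribution of the Wilcoxon statistic for 12 against 12 gives a two-sided size of 0.0449 when rejecting at U ≤ 37. At U ≤ 38 it is 0.0519, above 5%. One test therefore runs at about 4.5%.

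**4. False-positive rate if either window can be reported**

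This assumes no group difference, bivariate normal totals without ties, and rejection if either test rejects. The correlation ρ between the two totals is an assumption. Two independent tests at 4.49% would give 1 − (1 − 0.0449)² = 8.8%, a benchmark for the simulation.

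| ρ (assumed) | Either window significant |
|---|---|
| 0.5 | 8.3% |
| 0.8 | 7.3% |
| 0.95 | 6.1% |
| 0.99 | 5.3 to 5.4% |

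**5. Disagreement when the planned effect is real**

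With an effect size of 1.5 in both windows, each Wilcoxon test has about 92% power. The share of trials in which one test is significant and the other is not:

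| ρ (assumed) | Tests disagree |
|---|---|
| 0.5 | 12% |
| 0.8 | 8% |
| 0.95 | 5% |

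**6. Power if 1.5 belongs to one window only**

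If the other window has an effect size of 1.2 or 1.0 (both assumed), its Wilcoxon power is about 76% or 61%.

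A second route gives the same message. Suppose the other window adds an independent component with no group difference, whose standard deviation is k times the original. The effect size becomes 1.5/√(1 + k²):

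| k (assumed) | Effect size | t-test power |
|---|---|---|
| 0.25 | 1.46 | 92.6% |
| 0.5 | 1.34 | 88.1% |
| 1.0 | 1.06 | 70.0% |

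**The case against.** The strongest reply is that 48 hours is plainly what was meant. It stands under the Primary outcome heading, carries a written reason, and agrees with the Study Duration line and the 48-hour tracking of complications. The 24-hour phrase appears once, without a reason, and could be a drafting leftover. This is fair as a reading of intent. It is still inference: the analysis section calls its version the primary endpoint and is the text a statistician would execute. Nor would settling on 48 hours decide whether intra-operative opioid counts.

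The formula argument is supporting evidence only. A general conversion formula may list any opioid that could be given, including in the recovery unit, and the plan does not say that its as-needed list is complete.

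The numerical illustration also has limits, and these stand:

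- The windows share the first 24 postoperative hours. If only the 24 against 48 hour end differed, the correlation would probably be high and the inflation nearer 5 to 6%. A rate near 8% requires intra-operative opioid to contribute much of the variation.
- The inflation arises only if someone picks the window after seeing results. The plan does not propose this; it merely fails to prevent it.
- Simple randomization of 24 patients gives an exact 12–12 split in only C(24,12)/2²⁴ ≈ 16% of trials, and patients who need no opioid would create ties. The figures ignore both.

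Finally, the lack of a mean and standard deviation behind the effect size of 1.5 is a separate weakness that would remain after the window is fixed. It adds no weight here.

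**Conclusion.** The concern holds. The current text contains two incompatible definitions of the one primary endpoint and no rule of precedence, so the primary result is not uniquely determined by the plan. The contradiction itself needs no assumption.

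Its numerical consequence is conditional: a false-positive rate of roughly 5 to 8% in place of 4.5% if the window is chosen afterwards, and conflicting conclusions in roughly 5 to 12% of trials even when the planned effect is present in both windows. Those ranges rest on assumed correlations (0.5 to 0.99 for the first, 0.5 to 0.95 for the second), equal groups of 12, and normal data without ties. The power arithmetic is correct but cannot be assigned to either window. This must be fixed before any outcome data are reviewed, because it affects the trial's only powered comparison.

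**What to change.** Before outcome data are reviewed:

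1. Choose one primary window and state it in identical words under Primary outcome and Statistical Analysis. Which one is the sponsor's decision.
2. Say explicitly whether intra-operative opioid is included.
3. Label the other window as secondary or sensitivity.
4. In the sample-size paragraph, name the window to which the effect size of 1.5 refers.
5. If 48 hours is kept, state how opioid taken after discharge is counted and from what source, since the plan expects most patients to have left by then.

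The cost is protocol and SAP wording, with no extra patients. One of the two results loses primary status, and keeping 48 hours brings the added work of capturing opioid use after discharge.

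### The primary comparison of total opioid milligrams in children ignores body weight, so precision is lost if opioid use rises with weight

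*Combined protocol and SAP*

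**What the plan says.** - **Endpoint.** The Primary outcome paragraph compares the groups on "total narcotic dose in milligram morphine equivalents (MME". The formula adds micrograms of fentanyl, milligrams of hydromorphone and morphine, and a count of oxycodone tablet equivalents. It has no weight term.
- **Opioid use.** Under Research Design and Procedures, both groups have "oral oxycodone available as needed for moderate breakthrough pain and IV morphine for severe pain". No rule linking opioid dose to weight is given.
- **Population.** "Children undergoing pacemaker and/or Automatic Implantable Cardioverter Defibrillator implantation", without age or weight limits. The only age mentioned is 10 years, above which the patient's own consent is also sought, so children on both sides of 10 are evidently expected.
- **Allocation.** "The patients will be simply randomized by a pre-determined computer generated random numbers". No stratification is described.
- **Analysis.** Under Statistical Analysis, "Comparison between two groups will be evaluated by Wilcoxon rank sum test". Demographics are summarized only.
- **Weight elsewhere.** "The dose of 0.2% ropivacaine is 1ml/kg", so weight must be known for each patient.
- **Sample size.** "Based on a 5% two-sided two-sample t test", 12 per group give 94% power for "effect size 1.5 assuming that the primary endpoint follows a normal distribution". No SD, milligram difference or source is given, and nothing says whether variation in weight is included.

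**The concern.** In a population that may run from small children to near-adults, an opioid total in milligrams can differ between patients simply because of body size. If it does, the within-group spread contains a part unrelated to treatment. Simple randomization balances weight only on average, and even perfect balance would leave that spread in place. An unadjusted rank test then has to find the block effect against a noisier background.

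With 24 patients, and about 12 a year anticipated, lost precision cannot easily be bought back by enrolling more. At stake is the chance of detecting a real opioid-sparing effect, not the validity of a positive result.

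**Working it through.** **1. The plan's own figure.** Inputs from Statistical Analysis: n = 12 + 12, two-sided 5%, standardized effect d = 1.5. The noncentrality is 1.5 × √(12 × 12 / 24) = 1.5 × √6 = 3.67 on 22 df. Power from the noncentral t is 0.939, so the stated 94% reproduces.

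**2. What weight does to the effect size.** Let R² be the share of within-group variance explained by weight. If 1.5 was set free of weight variation, the unadjusted effect is 1.5 × √(1 − R²). If 1.5 is on total milligrams, the adjusted effect is 1.5 / √(1 − R²). Same t test, 22 df:

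| R² | Unadjusted power, 1.5 weight-free | Adjusted power, 1.5 on total mg |
|---|---|---|
| 0 | 93.9% | 93.9% |
| 0.1 | 91.5% | 95.9% |
| 0.3 | 83.6% | 98.7% |
| 0.5 | 70.0% | 99.9% |

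**3. The planned test, by simulation.** The documents give no weights and no opioid SD, so the following are assumptions.
- Per-patient dose d is normal with mean 1 and SD equal to the dose CV. It is 1.5 SD lower in the block group and truncated at 0.
- Weight W has mean 1 and is log-normal (or uniform 10–70 kg), independent of group.
- Total MME = d × W^p. Here p = 1 means use proportional to weight and p = 0 means unrelated.
- There are 12 per group and 40,000–60,000 trials per case.
- The exact Wilcoxon test rejects at U ≤ 37 or U ≥ 107, a level of 4.5%. The rank analysis of covariance regresses MME ranks on group and weight rank (21 df, 5%).

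| Case (dose CV 40%) | Wilcoxon, total MME | Wilcoxon, MME per kg | Rank ANCOVA on weight |
|---|---|---|---|
| Weight CV 50%, p = 1 | 75% | 92% | 88% |
| Weight CV 50%, p = 0.75 | 81% | 91% | 90% |
| Weight CV 50%, p = 0.5 | 87% | 87% | 90% |
| Weight CV 50%, p = 0 | 92% | 75% | 92% |
| Uniform 10–70 kg (CV 43%), p = 1 | 72% | 92% | 88% |
| Uniform 10–70 kg, p = 0.5 | 86% | 86% | 90% |
| Uniform 10–70 kg, p = 0 | 92% | 72% | 92% |

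Over weight CV 30–80%, dose CV 30–50% and p from 0 to 1, the ranges are 42–92%, 42–92% and 84–92%. The low corner for total MME (weight CV 80%, dose CV 30%, p = 1) gives 42%, against 84% with adjustment.

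**4. Checks.**
- The level of the rank analysis under the null is 4.8–5.2%.
- A rank test run at a full 5% gains only 1–2.5 points over the exact Wilcoxon, so most of the 13-point difference in the first row (75% to 88%) comes from the adjustment.
- With random group sizes under simple randomization of 24 patients, the first row becomes 73.5%, 90.7% and 86.7%.
- With 12 per group, the chance of a mean weight difference above 0.5 SD is 2 × [1 − Φ(0.5 / √(2/12))] = 22%.

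**5. Literal reading: 1.5 on total milligrams.** With weight CV 50%, dose CV 40%, p = 1 and SD proportional to the mean, the CV of the total is √(1.25 × 1.16 − 1) = 0.671. Solving r / (0.671 × √((1 + (1 − r)²)/2)) = 1.5 for the relative reduction r gives r = 0.74. With no weight variation the CV is 0.40 and r = 0.48.

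**The case against.** The strongest reply is that the premise is not in the documents. Opioids are given as needed, no per-kilogram opioid dose is stated, and per-kilogram local anesthetic says nothing about opioid demand. The sample-size sentence also attaches 1.5 to the primary endpoint, which is total milligrams. On that reading no power is lost. Both points are correct. They make the size of the problem conditional, and they leave unanswered how large an opioid reduction 1.5 SD of total milligrams represents.

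The gain can also be small. With weights of 40–70 kg and proportional use, power is about 89–90% unadjusted and 91% adjusted, a gap that the difference in test level can explain. With weight CV 50% and dose CV 60%, proportional use gives 84% and 89%. If an extra 20% of patients in each arm needed no opioid, both analyses would fall sharply, to about 38–39% and 45% in the proportional base case. Zeros would then cost more than weight. These cases limit the benefit but do not reverse it: adjustment was not materially worse in any case run.

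An unadjusted Wilcoxon test in a randomized trial is valid, and adjustment for efficiency is optional. That stands, and it is why this is a precision point only. A rank analysis of covariance gives no effect in milligrams, so the planned medians and boxplots are still needed.

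**Conclusion.** The concern holds. Neither the endpoint, the randomization nor the test takes account of weight, in a pediatric population with no stated limits. If opioid use rises with weight and 1.5 was set without weight variation, power falls below the stated 94%. It is about 72–75% in the proportional base cases and about 86–87% under square-root scaling. About 2 points of any shortfall from 94% reflect the Wilcoxon test itself, which has 92% power with no weight effect.

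If 1.5 refers to total milligrams, power is as stated but the detectable reduction is larger (74% against 48% under the assumptions above). The 94% is not miscalculated. The true loss cannot be derived from the documents. It is small if enrolled weights are similar or opioid use is only weakly related to weight.

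**What to change.** Before outcome data are examined, keep total MME as the endpoint and replace the unadjusted test under Statistical Analysis with wording such as:

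> Total MME and baseline body weight will each be ranked over all patients. The group effect will be tested by analysis of covariance of the MME ranks on group and weight rank (two-sided 5%). MME per kg will be compared by Wilcoxon rank sum test as a supportive analysis.

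Keep the planned median, inter-quartile and boxplot summaries. In the sample-size text, state the scale, SD and source of the 1.5. The new wording needs one defined time window. The Primary outcome paragraph (48 hours after the procedure) and Statistical Analysis (intra-operative plus the first 24 hours) differ, and that separate conflict must be settled too.

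MME per kg with the planned Wilcoxon test is an acceptable alternative only if the sponsor can document that use is close to proportional to weight. If use is unrelated to weight, dividing by it lowers power from 92% to about 75%.

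The cost is SAP wording and no additional patients. Weight is already needed to dose the ropivacaine. The sponsor should confirm that it is recorded for analysis before the paper data sheets are destroyed. If weight proves irrelevant, the adjustment costs under 1 point of power against the planned exact test.
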